### 3.1.2 TREATMENT LIMITING TOXICITY

Although not a phase 1 study, toxicity will be evaluated and treatment limited by the toxicities defined below. This study will utilize the CTCAE Common Terminology Criteria for Adverse Events (CTCAE) Version 4.0 for toxicity and Adverse Event grading and reporting. An adverse event must be judged to be possibly, probably, or definitely related to vandetanib to be a treatment limiting toxicity. Vandetanib will be held for treatment-limiting toxicities and re-started after resolution of toxicity at reduced dose as described in section 3.3.

Treatment-limiting toxicity is defined as:

- **Hematologic Toxicity (H-T):**
  - Neutrophil count below 1,000/ $\mu$ L (grade 3) on 2 consecutive measurements drawn at least 72 hours apart OR a single neutrophil count below 500/ $\mu$ L (grade 4).
  - Platelet count below 50,000/ $\mu$ L (grade 3) on 2 consecutive measurements drawn at least 72 hours apart OR a single platelet count below 25,000/ $\mu$ L (grade 4). A platelet transfusion administered when platelet count is below 50,000/ $\mu$ L is treatment -limiting thrombocytopenia, unless the transfusion is being administered for peri-operative coverage.
  - Grade 3 or 4 decrease in hemoglobin that can be corrected to at least 8.0 g/dl (grade 2) by transfusion of red blood cells is not a treatment-limiting toxicity. However, grade 3 or 4 hemolysis is a treatment -limiting toxicity if it is judged to be vandetanib-related.
  - Grade 3 or 4 leucopenia or lymphopenia will not be considered treatment -limiting toxicities.
- **Non-Hematologic Toxicity (NH-T):** NH-T is any grade 3 or higher non-hematologic toxicity, with the exception of:
  - Grade 3 nausea or vomiting that is controlled by symptomatic treatment with anti-emetics (see [Appendix 7](#) to avoid agents that can prolong the QTc) within 48 hours.
  - Any grade of diarrhea that is tumor-related (present at baseline and associated with elevated calcitonin levels) or grade 3 diarrhea that is related to vandetanib and is controlled by symptomatic treatment within 48 hours.
  - Grade 3 serum transaminase elevation (ALT/AST) that returns to grade 2 or less within 14 days. The drug may be held until the transaminase elevation subsides, but if the grade 3 transaminase elevation recurs when the drug is re-instituted, this will be considered treatment-limiting toxicity.

- Grade 3 electrolyte abnormalities that are asymptomatic and correctable to grade 2 or less within 48 hours.

- **Hypertension (HTN):**

- **Pediatric Participants:**

For pediatric patients, the ULN for blood pressure is defined as a diastolic BP at the 95th percentile from age and gender-appropriate normal values (see [Appendix 2](#)). Pediatric patients with a diastolic blood pressure >95% for age and gender should have blood pressure measurement repeated x2 with an appropriate size cuff, and hypertension (HTN) is defined as at least 2 (of 3) measurements exceeding the ULN (See [Appendix 2](#) and [Appendix 3](#)). Treatment-limiting hypertension is defined as:

- A diastolic BP on at least 2 of 3 measurements that is more than 25 mm Hg above the ULN for age and gender.
- A diastolic BP on at least 2 of 3 measurements that is above the ULN but not more than 25 mm Hg above the ULN and that does not return to within the normal range after 14 days on single agent antihypertensive therapy.
- Grade  $\geq 4$  (CTCAE v.4) hypertension.

- **Adult Participants:**

[Appendix 4](#) will be used for the grading of vandetanib-associated hypertension in adults, for immediate and intermediate-term management, and for the determination of vandetanib modification. Hypertension in adult patients is defined as a systolic blood pressure > 150 mmHg or a diastolic pressure > 90 mm HG despite optimal medical management, for patients  $\geq 18$  years of age, and may include hypertension-related symptoms as reported by patient (e.g., headache), or other relevant changes associated with development of hypertension (e.g., ECG abnormalities) (See [Appendix 4](#) and [Appendix 5](#)).

Treatment-limiting hypertension is defined as:

- A diastolic BP on at least 2 of 3 measurements that is more than 90 mm Hg or systolic BP that is more than 150 mm Hg, that does not return to within the normal range after 14 days despite maximum medical therapy.
- Grade  $\geq 4$  (CTCAE v.4) hypertension.

- **QTc Prolongation:**

Any clinically significant abnormal findings or QTcB prolongations will be recorded as AEs.

Participants with QTc prolongation should have serum electrolytes (including potassium, calcium and magnesium) measured. If serum electrolytes are outside the normal range, the abnormality should be corrected before determining whether a patient has treatment-limiting QTc prolongation.

In addition to scheduled ECG, additional ECGs should also be performed in the event of QTcB prolongation, both during and post the prolongation period.

- During the QTcB prolongation period: For a single QTcB value of >500 ms, vandetanib must be withheld. Electrocardiograms will be followed at least once per week (done at the same day each week) along with electrolytes, until QTcB falls  $\leq 480$  ms. Vandetanib treatment may be resumed at a permanently lower dose after the QTcB returns to  $\leq 480$  ms.

Treatment-limiting QTc prolongation is defined as a single QTc value  $\geq 500$  msec. Post the QTcB prolongation period: If vandetanib (at the reduced dose) is restarted after the QTcB prolongation has resolved, ECGs and electrolytes (including potassium, calcium and magnesium) must be obtained at 3, 8, and 12 weeks following the start of the lower dose. Serum potassium levels should be maintained at 4 mEq/L or higher, and serum magnesium and serum calcium should be kept within normal range to reduce the risk of QT prolongation. ECG and electrolyte monitoring can then resume every 3 weeks at the normal visit schedule for the patient.

If a patient is on 100 mg vandetanib dose and has QTcB >500 ms, vandetanib 100 mg may be given every other day.

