### 3.3 DOSE MODIFICATIONS

#### 3.3.1 GENERAL GUIDANCE

Vandetanib should be held for any treatment-limiting toxicity (see Section 3.1.2). For treatment limiting toxicities that include a duration in the definition, such as a neutrophil count below 1,000/ $\mu$ L (grade 3) on 2 consecutive measurements drawn at least 72 hours, the drug will be held after the toxicity reaches the grade defined in treatment limiting (e.g., after the second ANC <1,000/ $\mu$ L).

If vandetanib-related treatment-limiting toxicity resolves to grade  $\leq$ 1 or baseline in  $\leq$ 6 consecutive weeks of drug free period, vandetanib may be restarted at a reduced dose.

If the vandetanib-related treatment-limiting toxicity does not resolve to grade  $\leq 1$  or baseline in  $\leq 6$  consecutive weeks of a drug free period the patient should discontinue protocol therapy and be monitored until the toxicity resolves.

The cycle duration remains 28 consecutive days in patients who have dose interruptions.

If a patient happens to miss 6 weeks of dosing for non-toxic events, if monitoring is initiated as described in Section 3.5.1, the patient may initiate re-dosing.

Refer to Section 4 Concomitant Medications/Measures for management of specific toxicities.

Refer to Section 3.1.1 for intra patient dose escalations.

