### 3.3.2 DOSE MODIFICATION RULES

The NCI Principal Investigator should be consulted for all dose reductions. Dose modifications will be conducted according to the following guide:

- Patients who experience a treatment-limiting toxicity (Section 3.1.2) that is possibly, probably, or definitely related to vandetanib should have a dose reduction of their vandetanib dose after recovery from toxicity (to a CTCAE Grade 1 or baseline) (Section 3.2 Drug Administration) following the table below for the remainder of the current course and for the subsequent cycles of treatment.

Vandetanib starting dose (mg/dose) once daily	Dose reduction (mg/dose)	Dose reduction (%)
50	50 mg 5 times/week (e.g. Monday, Tuesday, Thursday, Friday, Sunday)	29%
100	100 mg 5 times/week (e.g. Monday, Tuesday, Thursday, Friday, Sunday)	29%
150	100 daily	33%
200	200 mg 5 times/week (e.g. Monday, Tuesday, Thursday, Friday, Sunday)	29%
250	200 mg 6 times/week (Monday, Tuesday, Wednesday, Thursday, Friday, Saturday)	40%
300	200 daily	33%

- Patients who experience treatment-limiting toxicity after a dose reduction can have one additional dose reduction. All dose reductions should be approximately 30% of the administered dose. The protocol PI or lead AI should confirm the dose reduction.

- Patients who have a dose reduction for a non-life-threatening treatment-limiting toxicity (diarrhea, nausea, vomiting, constipation, anorexia, weight loss, fatigue or skin rash) and who tolerate  $\geq 2$  cycles at the reduced dose can have their dose re-escalated to the prior dose level. The toxicity type that was previously treatment-limiting toxicity at the higher dose level must not have exceeded grade 1 at the reduced dose level in order to re-escalate the dose.

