### Management of Hypertension in Adults

BP measurements - systolic/diastolic	Interval	Treatment/Dose Modification
Patients not receiving maximal antihypertensive therapy:		
≥ 150 mmHg (systolic) OR ≥ 100 mmHg (diastolic)	2 BP readings at least 1 hour apart	
 
• Add new or additional antihypertensive meds or increase dose of existing meds
 
• Maintain dose of vandetanib
 

> 200 mmHg (systolic) OR > 110 mmHg (diastolic)	2 BP readings during a 1-week period	
 
• Hold vandetanib
 
• Monitor patient closely for hypotension (if on antihypertensive meds) until vandetanib is restarted.
 
• Resume treatment when BP falls to <150/100
 

Patients receiving maximal antihypertensive therapy*:		
> 160 mmHg (systolic) OR > 105 mmHg (diastolic)	2 BP readings at least 1 hour apart	
 
• Hold vandetanib
 
• Maintain antihypertensive meds and monitor patient closely for hypotension until vandetanib is restarted.
 
• Resume treatment at one lower dose level when BP falls to <150/100
 

* Maximal antihypertensive therapy is defined as four antihypertensive medications given for 2 weeks.		

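### For adults on maximal antihypertensive therapy, the treatment-limiting definition in 3.1.2 and the hold limits in Appendix 4 conflict over a band of pressures, and no sentence reconciles them; one dose-reduction percentage and the diary's missed-dose limit also need correcting

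*Combined protocol and SAP*

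**What the plan says.** **Adult hypertension, Section 3.1.2.** The adult paragraph first names Appendix 4 for grading, "for immediate and intermediate-term management, and for the determination of vandetanib modification". It then gives its own treatment-limiting definition, judged at 14 days of maximum medical therapy: diastolic "more than 90 mm Hg or systolic BP that is more than 150 mm Hg, that does not return to within the normal range". The sentence also asks for at least 2 of 3 measurements; whether that applies to systolic as well as diastolic pressure is open to reading.

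**Consequence of a treatment-limiting toxicity.**
- Section 3.1.2: "Vandetanib will be held for treatment-limiting toxicities and re-started after resolution of toxicity at reduced dose as described in section 3.3".
- Section 3.3.1: "Vandetanib should be held for any treatment-limiting toxicity (see Section 3.1.2").
- Section 3.1.3.2: the dose is to be modified under 3.3.
- Section 3.3.2: such patients "should have a dose reduction of their vandetanib dose after recovery from toxicity (to a CTCAE Grade 1 or baseline").

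None of these excepts hypertension. Section 3.3.1 does refer to Section 4 for managing specific toxicities, and 4.2 sends hypertension to Appendices 2 and 4.

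**Appendix 4, adults on maximal therapy.** Hold at "> 160 mmHg (systolic") or "> 105 mmHg (diastolic"), on two readings at least one hour apart. "Resume treatment at one lower dose level when BP falls to" below 150/100. Maximal therapy means four drugs for two weeks.

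**Two unrelated items.** The 3.3.2 table reduces 250 mg daily to 200 mg on six days a week and prints 40%. Section 3.2 has a missed dose taken if it is less than 12 hours late; the diary in Appendix 8 tells the patient not to take it after 6 hours.

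**The concern.** Two rules in one protocol give different pressures for stopping the drug in the same patients. In the band between them, a clinician who applies the 3.1.2 definition with the general hold rule stops vandetanib and restarts it lower. One who applies the Appendix 4 table continues at full dose.

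The label has consequences beyond dosing. Section 7.1.10 requires a telephone report of a related treatment-limiting toxicity within 24 hours, and 3.6.1 removes a patient from therapy for such a toxicity after two dose reductions. If Appendix 4 alone decides the hold, the same event is still a reportable treatment-limiting toxicity while dosing continues. Safety is a secondary objective, summarised descriptively under 8.2, so a reader of that summary needs to know which definition was used.

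The other two items are smaller. The percentage cell contradicts the schedule beside it. The diary, which patients use at home, tells them to skip a dose that 3.2 says to take.

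**Working it through.** **1. Hold limits side by side (adults on maximal antihypertensive therapy)**

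| | 3.1.2 with 3.3.1 | Appendix 4 |
|---|---|---|
| Systolic | above 150 | above 160 |
| Diastolic | above 90 | above 105 |
| Readings | at least 2 of 3 (scope unclear) | two, at least 1 hour apart |
| Duration | not normal after 14 days on maximum therapy | none beyond the two weeks in its definition of maximal therapy |
| Maximal therapy | not defined | four drugs for two weeks |
| Restart | grade 1 or less, or baseline | below 150/100 |
| Dose after hold | reduced | one level lower |

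Assumption: the normal range in 3.1.2 is 150/90 or below. That bullet does not define it. The same section defines adult hypertension as above 150 or above 90, which makes the assumption natural but does not settle it. A lower normal range would extend the band downwards; its upper edge comes from Appendix 4 and would not move.

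Band, in whole mmHg, where 3.1.2 is met and Appendix 4 is not, for a related event that has persisted for 14 days, with neither value above the Appendix 4 limits:
- systolic 151 to 160: 160 − 150 = 10 values
- diastolic 91 to 105: 105 − 90 = 15 values

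It is not stated whether the 14 days in 3.1.2 are the same two weeks as in Appendix 4 or come after them. The restart difference cannot be sized, because the CTCAE cut-offs are not in the documents and baseline differs by patient.

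**2. Dose consequence in the band (3.3.2 table, adult at an unreduced dose)**

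Reduction = 1 − (reduced mg × days per week) / (7 × starting mg).
- 200 mg daily: 7 × 200 = 1400 mg a week; reduced 5 × 200 = 1000; 1 − 1000/1400 = 28.6%.
- 300 mg daily: 7 × 300 = 2100; reduced 7 × 200 = 1400; 1 − 1400/2100 = 33.3%.

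Under Appendix 4 the same adult stays at 1400 or 2100 mg a week. The days lost to the hold come on top.

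**3. The 250 mg row**

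The formula reproduces the table's other five rows: 28.6% at 50, 100 and 200 mg (printed 29%), and 33.3% at 150 and 300 mg (printed 33%). For 250 mg: 6 × 200 = 1200 of 7 × 250 = 1750; 1 − 1200/1750 = 31.4%, printed 40%, a gap of 8.6 points. A cut of exactly 40% would be 150 mg daily (1 − 1050/1750). Section 3.3.2 asks for reductions of about 30%, which fits the printed schedule. The 250 mg dose arises only in children at 150 mg/m² with a BSA of 1.5-1.83 m², from cycle 4.

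**4. Missed dose**

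The two texts disagree for doses more than 6 and less than 12 hours late.

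**The case against.** The strongest reply is that the protocol does say where to look. The adult paragraph of 3.1.2 assigns vandetanib modification to Appendix 4, and 3.3.1 refers to Section 4, whose 4.2 leads there too. On the usual principle that a specific rule overrides a general one, Appendix 4 governs. This largely stands. A reader might infer that the protocol is silent on precedence; the documents do not support that.

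The pointers still do not remove the conflict. The one in 3.1.2 sits directly above a separate treatment-limiting definition, and the orders in 3.1.2, 3.1.3.2 and 3.3.1 attach a hold or dose change to any event that meets it. By contrast, the paediatric definition and Appendix 3 share the 25 mmHg margin and the 14 days on a single agent, so the adult mismatch looks like an oversight.

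It is also fair to say that reach is narrower than the band. Appendix 4 adds drugs only from 150 systolic or 100 diastolic, so diastolic 91-99 alone, 9 of the 15 values, would not bring a patient to four drugs under that table. Earlier higher readings or other grounds would be needed. The principal investigator is consulted on all dose reductions, which limits the effect further.

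Finally, the written schedule, not the percentage, sets the 250 mg dose, so that cell is close to clerical. The diary is the more cautious of the two missed-dose texts. Both objections are accepted as to size.

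**Conclusion.** The texts contradict each other, and the point is minor. Section 3.1.2 and 4.2 point to Appendix 4 for adult hypertension, but the 3.1.2 definition with the general hold orders produces a lower limit, and no sentence reconciles them. The disagreement covers 10 mmHg systolic and 15 mmHg diastolic, and a difference of 28.6% or 33.3% in weekly dose after restart. It rests on reading the normal range as 150/90 or below and applies only to related hypertension that has persisted for 14 days on maximum therapy.

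Reach is small. Section 8.3 says accrual closed with nine patients. The number of adults is not given, so no count can be derived, and it may be zero. A reader might infer that some adults were dosed wrongly; the documents give no evidence of that.

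Nor is this a flaw in the response design: the stage sizes, stopping rule and error rates in 8.1 use none of these rules. For the 250 mg row, the percentage is the likelier error, but the documents do not prove which entry is wrong.

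**What to change.** - Add one sentence to 3.1.2 saying that Appendix 4 governs the adult hypertension hold, restart and dose change; or set the Appendix 4 limits to those of 3.1.2. The clinical team chooses the values.
- Use one set of thresholds, one reading rule and one definition of maximal therapy in both places, and define the normal range.
- State in the safety summary which definition was applied to treated adults, or that none fell in the band.
- Align the diary's 6 hours with the 12 hours in 3.2, after the sponsor confirms that 12 is intended.
- Change 40% to 31% in the 250 mg row, after confirming the six-times-weekly schedule.

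The cost is a few text edits, one table cell, one diary line and one sentence of reporting. Sample size and the primary analysis do not change. If no patient remains on treatment, only the safety-summary sentence has practical effect.

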### 3.1.3 CRITERIA FOR STARTING SUBSEQUENT TREATMENT CYCLES

Patients who complete a treatment cycle (28 days) may receive another cycle if:

- 3.1.3.1 Disease Status: The patient does not have radiographic or clinical evidence of progressive disease (see section 6.3) for cycles prior to which the patient is re-staged, or in the opinion of the investigator the patient is benefiting from the therapy with vandetanib as evidenced by stable or decreased tumor-related symptoms such as pain, nausea or vomiting, or stable for cycles that are not preceded by restaging.
- 3.1.3.2 Toxicity: Patients who experienced treatment-limiting toxicity in the previous cycle should have the dose modified (see Section 3.3).
- 3.1.3.3 Criteria for discontinuation of protocol treatment or off-study criteria (see Section 3.6) have not been met.

There is no limit on the number of cycles that a patient may receive.

Criteria for intra patient dose escalation after completion of cycles 1, 2, and 3 of vandetanib are provided in Section 3.1.1.

## 3.2 DRUG ADMINISTRATION

Vandetanib (50 mg and 100 mg tablets) is administered orally, once daily continuously. A cycle of vandetanib is defined as 28 consecutive days starting with the first day of treatment (day 1). Patients 18 years or older at the time of enrollment on this study will receive a fixed initial dose of 200 mg orally daily, which can be increased to 300 mg orally daily after 3 cycles, if tolerated (Section 3.1.1). The dose of vandetanib in children and adolescents is determined from the patient's body surface area using the dosing nomogram below. The BSA should be recalculated at the time of restaging evaluations, and the dose should be adjusted if necessary based on the nomogram. Treatment will be administered in an outpatient setting.

Dose Level (mg/m  )						
100	BSA (m  )	0.50-0.74	0.75-1.24	1.25-1.74	≥ 1.75	
	Dose (mg)	50	100	150	200	
150	BSA (m  )	0.50-0.83	0.84-1.16	1.17-1.49	1.5-1.83	≥1.84
	Dose mg)	100	150	200	250	300

Vandetanib is supplied as 50 and 100 mg tablets. Vandetanib should be stored at room temperature in the original pack until use.

Patients will receive their assigned dose of vandetanib once daily at the same time of the day (An every other day dosing schedule can be used to achieve lower dose levels in patients requiring a dose reduction, see Section 3.3). Vandetanib absorption is not affected by a meal, so it need not be administered in the fasted state.

The tablet should be swallowed whole or dissolved in water (see Section 11.1.5). If a patient misses a scheduled dose of vandetanib and less than 12 hours have passed since the scheduled dosing time, the dose should be taken immediately. If more than 12 hours have passed since the scheduled dosing time, the patient should not take the missed dose but should wait and take the next regularly scheduled dose.

If the patient vomits within 30 minutes of taking vandetanib, then another dose can be administered. The dose may only be repeated once. If more than 30 minutes has passed from the time of oral dosing then no additional doses should be given.

Patients or their guardians will keep a diary (Appendix 8) to document the intake of each dose, concomitant medications, and any toxicity. The diary should be evaluated at each clinic visit. Self-Administered Study Drugs: Policy, procedures and forms are available on the CCR Intranet for internal monitoring for study drug compliance and accountability at the CCR Intranet site: [http://home.ccr.cancer.gov/intra/clin\\_ops/policies/](http://home.ccr.cancer.gov/intra/clin_ops/policies/).

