### 1.2.2 VANDETANIB

Vandetanib (CAPRELSA®; ZD6474; AstraZeneca, Macclesfield, UK) is a small molecule receptor tyrosine kinase (RTK) inhibitor, given as a once-daily oral drug that inhibits VEGFR2- and EGFR- dependent signaling. It is also potent inhibitor of RET, which is frequently activated by mutation or rearrangement in medullary thyroid carcinoma (MTC)(20). Vandetanib has activity in MTC in adults at doses ranging from 100 to 300 mg once daily on a continuous dosing schedule and in children receiving 100 mg/m^2/dose (equivalent to 180 mg fixed dose based on a BSA of 1.8 m^2), or 150 mg/m^2/dose (equivalent to 270 mg fixed dose). At this time the active dose in children with GIST is unknown; we therefore will use the highest tolerable dose evaluated in children: 150 mg/m^2/dose for children 13 years and older, and 100 mg/m^2/dose with option for dose escalation to 150 mg/m^2/dose for children less than 13 years old. In children and adults with MTC vandetanib has been well tolerated with prolonged administration with diarrhea, rash, and TSH elevation being the most frequent toxicities. Tumor shrinkage is occurring slowly over multiple treatment cycles(20, 21).

Vandetanib is currently undergoing evaluation in a phase II trial for patients with clear cell renal cell carcinoma at the NCI based on concomitant VEGFR and EGFR inhibition(18). Preliminary data from this trial demonstrate marked growth inhibition of SDH-mutant/deficient RCC when treated with vandetanib. Thus, there might be a role for vandetanib in the treatment of wt-GIST and SDH mutations.

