# 3 STUDY IMPLEMENTATION

## 3.1 STUDY DESIGN

### 3.1.1 STUDY OVERVIEW

This phase II trial is designed to determine whether daily oral vandetanib is active (clinical activity as per RECIST v1.1) in patients with wt- GIST. Vandetanib activity will be primarily assessed by response of measurable disease using RECIST (v1.1), but change in tumor-related symptoms from baseline will also be monitored to assess drug effect.

Adults and children (patients older than 3 years) with measurable wt-GIST will be eligible for trial participation. Patients must have measurable disease by RECIST and adequate organ function.

Vandetanib will be administered orally once a day on a continuous dosing schedule. One treatment cycle equals 28 days.

- Patients 18 years and older at the time of enrollment on this study will start vandetanib at a fixed dose of 200 mg once daily (QD) for cycles 1, 2, and 3.

- Patients younger than 18 years of age at the time of enrollment will start vandetanib at a dose of 100 mg/m^2/dose for cycles 1, 2 and 3. (see table below).

Table 1: Vandetanib Dose Escalation Schedule	
Age at Enrollment	Daily Dose of Vandetanib
Patients < 18 years of age	Cycles 1-3: 100 mg/m  /dose
	If vandetanib is well tolerated : Cycles ≥4: 150 mg/m  /dose
Patients ≥ 18 years of age	Cycles 1-3: 200 mg/dose
	If vandetanib is well tolerated : Cycles ≥4: 300 mg/dose

A one time intra patient dose escalation to 150 mg/m^2/dose for patients < 18 years, and to 300 mg/dose for patients ≥ 18 years will be allowed after completion of 3 cycles, provided provided the intra patient dose escalation criteria below are fulfilled:

Vandetanib is well tolerated at the starting dose defined as:

- All vandetanib related toxicities during cycle 1-3 are less than grade 2, except grade 2 toxicities that are:
  - isolated laboratory abnormalities and not present at repeat blood draw, or
  - short lived and resolve within approximately 72 hours with or without supportive therapy.

There is no limit on the number of cycles that a patient may receive. The dosing nomogram provided in section 3.2 will be used to determine the vandetanib dose for pediatric patients.

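### The pediatric nomogram and the stated 100 to 150 mg/m² escalation do not agree: the dose step given ranges from 0% to +100% depending on BSA

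*Combined protocol and SAP*

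**What the plan says.** Section 3.1.1 says that patients under 18 "will start vandetanib at a dose of 100 mg/m 2 /dose for cycles 1, 2 and 3". It then allows, subject to tolerability criteria for cycles 1-3, "A one time intra patient dose escalation to 150 mg/m 2 /dose for patients < 18 years". The arms table in Section 2.4 gives the same two levels.

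The tablet dose comes from Section 3.2. Section 3.1.1 refers to it directly: "The dosing nomogram provided in section 3.2 will be used to determine the vandetanib dose for pediatric patients". Section 3.2 says the same: "The dose of vandetanib in children and adolescents is determined from the patient's body surface area using the dosing nomogram below". The table has one row per level, with different BSA bands. The 100 mg/m² row uses "0.50-0.74 0.75-1.24 1.25-1.74" and then 1.75 and above, for 50, 100, 150 and 200 mg. The 150 mg/m² row uses "0.50-0.83 0.84-1.16 1.17-1.49 1.5-1.83" and then 1.84 and above, for 100, 150, 200, 250 and 300 mg. Tablets are 50 and 100 mg. Section 2.1.1.1 admits patients from 0.5 m², so every band is open to eligible children.

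Section 1.2.2 supports the pediatric dosing by saying that "we therefore will use the highest tolerable dose evaluated in children"; the top level it names is 150 mg/m². On reductions, Section 3.3.2 says "All dose reductions should be approximately 30% of the administered dose", and it permits one further reduction after the first.

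**The concern.** A reader of Sections 2.4 and 3.1.1 would expect a child who meets the tolerability criteria to receive half as much again from cycle 4. Because the band edges differ between the two rows, a child can instead sit in the same tablet dose on both rows, or jump two tablet steps at once.

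Two consequences follow. For safety, some children would move to a dose twice the one on which tolerability was judged, and the smallest could receive more per m² than the level cited as support. For reporting, the nominal level does not identify, or even order, the dose received. That matters for the secondary objective of describing safety at established doses (Section 1.1.2.1), above all in a study in which Section 8.3 records nine enrolled patients.

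**Working it through.** **Inputs.** The two nomogram rows (Section 3.2), levels 100 and 150 mg/m² (Section 3.1.1), minimum BSA 0.50 m² (Section 2.1.1.1), and the reduction table (Section 3.3.2). BSA is taken to two decimals, as printed, and held fixed across the step.

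**Reproducing the nomogram.** Tablet dose = level × BSA, rounded to the nearest 50 mg with ties rounded up. Examples: 100 × 0.74 = 74, giving 50 mg; 100 × 0.75 = 75, giving 100 mg; 150 × 0.83 = 124.5, giving 100 mg; 150 × 0.84 = 126, giving 150 mg. At every 0.01 m² from 0.50 to 1.83, both rows match the printed doses without exception.

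**Planned step.** 150/100 − 1 = +50%.

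**Step delivered.** Change = (dose on 150 row)/(dose on 100 row) − 1. Delivered dose = tablet dose/BSA, shown from the lower to the upper end of each band.

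| BSA (m²) | 100 row (mg) | 150 row (mg) | Change | Delivered, 100 row (mg/m²) | Delivered, 150 row (mg/m²) |
|---|---|---|---|---|---|
| 0.50-0.74 | 50 | 100 | +100% | 100.0 to 67.6 | 200.0 to 135.1 |
| 0.75-0.83 | 100 | 100 | 0% | 133.3 to 120.5 | 133.3 to 120.5 |
| 0.84-1.16 | 100 | 150 | +50% | 119.0 to 86.2 | 178.6 to 129.3 |
| 1.17-1.24 | 100 | 200 | +100% | 85.5 to 80.6 | 170.9 to 161.3 |
| 1.25-1.49 | 150 | 200 | +33% | 120.0 to 100.7 | 160.0 to 134.2 |
| 1.50-1.74 | 150 | 250 | +67% | 100.0 to 86.2 | 166.7 to 143.7 |
| 1.75-1.83 | 200 | 250 | +25% | 114.3 to 109.3 | 142.9 to 136.6 |
| 1.84 and above | 200 | 300 | +50% | 108.7 at 1.84, then falling | 163.0 at 1.84, then falling |

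**Largest excess.** 100/0.50 = 200 mg/m², and 200/150 − 1 = +33%. In the lowest band the delivered dose passes 150 mg/m² up to BSA 0.66 (100/0.66 = 151.5) and not at 0.67 (100/0.67 = 149.3).

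**Ordering.** A child of BSA 0.75 at level 100 receives 133.3 mg/m². A child of BSA 0.83 at level 150 receives 120.5 mg/m².

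**Reductions after a doubling.** From 50 to 100 mg: the first reduction is 100 mg five times a week, 100 × 5/7 = 71.4 mg/day, and 71.4/50 = 1.43, or 43% above the earlier dose. A second reduction of about 30% gives 71.4 × 0.7 = 50.0 mg/day. From 100 to 200 mg: 200 × 5/7 = 142.9 mg/day, again 43% above; then 142.9 × 0.7 = 100.0 mg/day.

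**The case against.** The strongest reply is that this is what whole tablets do. Section 3.2 discloses the tablet sizes, Section 3.1.1 makes the nomogram operative, and no section prints a figure of +50% or promises the same step to every child. With once-daily whole 50 mg tablets, a child on 50 mg can only stay there or at least double. All of this stands, and it means that the nomogram contains no arithmetic error, although a reader might infer one. It does not remove the disagreement. The protocol names two levels, makes escalation conditional on tolerability, and does not acknowledge that in one band the levels coincide and in two the dose doubles.

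Four stronger inferences are tempting and are not supported:

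- **That safety or activity by dose cannot be read.** Section 8 plans no analysis by dose level. Dose taken (diary, Appendix 8) and BSA at each restaging (Section 3.5.1.3) are recorded, so delivered dose can be derived.
- **That the reduction rules never undo a doubling.** This is true of the first reduction only; the second brings the average back to about the earlier dose.
- **That small children exceed the exposure actually studied.** The 150 mg/m² in Section 1.2.2 is a nominal level. The documents do not give the tablet rounding or delivered doses of the pediatric trial behind it. The excess shown here is over the nominal level.
- **That enrolled children were mis-dosed or misclassified.** Section 8.3 gives no breakdown by age or BSA, and the documents do not say whether the database records level or milligrams.

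**Conclusion.** The point holds as a conflict between stated rules, with a consequence for dosing safety and for reporting. Following the plan as written, an eligible child's escalation step is anywhere from 0% to +100%. It equals the +50% implied by Sections 2.4 and 3.1.1 in two of eight bands, 0.84-1.16 and 1.84 and above. At 0.75-0.83 it is nil, and at 0.50 the 150 row gives 200 mg/m², a third above the nominal level that Section 1.2.2 cites.

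The figures assume an unchanged BSA across the step. Section 3.2 has BSA recalculated at restaging, which also falls before cycle 4, so a child who crosses a band edge then would have a different step. The primary two-stage rule counts pooled complete and partial responses and does not use dose, so its error rates are untouched. How many children are affected cannot be determined from the documents. The point should be settled, but it does not threaten the primary analysis.

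**What to change.** The clinical team should reconcile Sections 2.4, 3.1.1 and 3.2, checking the result against the dose rationale in Section 1.2.2 and the reductions in Section 3.3.2, or state in the protocol that the band-dependent steps are intended. No dose, band or limit is proposed here.

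For children already treated, derive delivered mg/m²/day from the recorded dose and BSA and report it beside the safety summaries in Section 8.2. From cycle 13 the intake data come from patient interviews rather than the diary (Appendix 9), so the derivation should name its source. Do not describe a child whose tablet dose did not change as escalated.

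The cost is a text amendment and one derived variable from data already collected, with no extra patients or procedures. If the clinical team decides to change the table itself, that work is additional: in the lowest band the tablet sizes leave no intermediate once-daily step.
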